The primary recruitment site for both aims will be Lumumba Sub-County Hospital (“Lumumba Clinic”), which is located next door to the RCTP. PrEP is included in the Kenyan National HIV Prevention Revolution Road Map [34], in which young women are identified as a priority population, and available at no charge through Lumumba Clinic and other public facilities. A total of 438 young women have received PrEP at this facility, making recruitment highly feasible. Contraception and STI testing/treatment (typically in the setting of symptoms, not routine screening) are also available free of charge. Recruitment may also occur through Kisumu County Hospital, which has a similar clinic and is located a 5 minutes-drive from our study offices.

Aim 1. Develop the *PrEP My Way* intervention

Overview. Using a client-centered approach, we will create a young woman-centered kit consisting of HIV self-testing, PrEP refills, STI self-sampling, and pregnancy tests and contraception (if desired), along with educational materials and kit delivery protocols for peer delivery in the community. We will hold individual interviews and focus group discussions with Kenyan women (age 16-24) in an iterative manner to optimally design *PrEP My Way* (the kit with instructional materials) and peer delivery system (including phone-based communication and kit delivery plans).

The intervention. *PrEP My Way* will be developed through an iterative, client-centered process. However, we anticipate that it will involve one clinic-based visit to safely initiate PrEP and contraception per Kenyan national guidelines [35], followed by quarterly community-based peer delivery of a pre-packaged, visually-appealing kit with pictorial and video guidance (to be

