Recruitment. We will identify young women to participate in the pilot RCT at the time they initiate PrEP at the Lumumba Clinic or Kisumu County Hospital. Participants may also be identified in the nearby community and invited to attend either facility to initiate PrEP and enroll in the study. Community recruitment will be done in areas such as hotspots, fish landing points, and within the general low end estates with the help of community health volunteers. These participants will be distinct from those engaged in the development of the intervention (Aim 1) to increase likelihood of generalizable findings. Similar to Aim 1, participants will be approached randomly (e.g., the second client seen on a given day) with stratification by age (16-20 versus 20-24). Only up to three participant will be enrolled per site per day to avoid clustering effects, as young women often present for PrEP services in groups [40].

Figure 4. Participant flow for the pilot RCT of *PrEP My Way* versus standard of care

Consent, enrollment, and randomization. Eligibility criteria for the pilot RCT participants are as follows. All participants will have started PrEP within the past two weeks:

- Inclusion criteria
 - Young woman (age 16-24 years); we will enroll emancipated minors (e.g., those who have not yet attained the age of legal competency as defined by state law, but who are entitled to treatment as if they had by virtue of assuming adult responsibilities, such as self-support, marriage, or procreation) per Kenyan national guidelines [39] or 16-17 year-olds with parental/caregiver consent
 - Initiating PrEP (this criterion subsumes all necessary safety assessments for starting PrEP, including HIV-negative status, normal renal function, and lack of Hepatitis B infection)
 - Reported sexual activity in the past 3 months
 - Residence in the Kisumu region (maximum of 20 km from our study offices at RCTP)
 - Phone ownership
 - Ability to understand KiSwahili, DhoLuo, and/or English

- Exclusion criteria- inability to provide informed consent (e.g., intoxication, mental disability)

Note: Participants may also be excluded at the discretion of the principal investigator (e.g., because of co-enrollment with a study that would compromise study aims or disruptive behavior).

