At kit delivery, the peer will guide the participant through the pictorial materials for each aspect of the kit and show her the video. HIV test results will be available at the time of testing. The peer can be present to see the test results or not, per the participant's preference. She will answer any questions regarding the kit and its components; any challenging questions will be brought back to clinical staff at the RCTP study site and answers relayed to the participant via phone. The peer may also provide weekly empowerment messages (e.g., "Remember- PrEP gives you control over your sexual health") via phone; participants will be able to opt out of these messages, if desired (e.g., for privacy). The peer will obtain the HIV test results and document PrEP and contraception use. She will bring the vaginal swab back to the study site for processing. The peer will also dispose of any remaining materials, if desired by the participant. The peer will send an SMS or WhatsApp message indicating either normal results or the need for the participant to come to the study site for abnormal or indeterminate results within a few days. Explicit mention of STI testing will not occur in the messages to protect the participant's privacy of the participants. Treatment and supportive counseling will then be provided by our staff per Kenyan national guidelines [35]. Arrangements will be made for prompt repeat HIV testing at our study site if any of the self-testing kits reveal a positive or indeterminant result; linkage to free antiretroviral therapy services will be facilitated in the event of a confirmed seroconversion. Participants will be offered repeat STI testing in the clinic if their self-collected samples are inadequate for testing. Follow-up for any other concerning situations (e.g., social harms) will be arranged by study staff as appropriate (see *Human Subjects*).

[figure not shown]
At completion of the visit, the peer will make tentative plans for a repeat visit in two months (Month 3 of PrEP). She will remind the participant that she is available via mobile phone for any *PrEP My Way*-related questions and support. She will then contact the participant one week in advance of the tentative visit appointment to confirm it or make any necessary adjustments. Scheduling will aim to avoid any lapses in PrEP coverage and will occur in a private location during reasonable working hours, as described above.

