The above-noted procedures will be repeated at the Month 3 and Month 6 visit. Additionally, at the Month 6 visit, an RA will collect the following data either in the field or at the study site (within the next two weeks):

- Dried blood spot for tenofovir concentration
- Creatinine (point-of-care)
- Socio-behavioral data (quantitative questionnaire; see Table 1)
- Acceptability data (see below)

Acceptability will be determined quantitatively with the Systems Usability Scale (SUS; [49]). This 10-item Likert scale assesses domains including desired frequency of use, complexity, need for support, functionality, irregularities, ease of learning/use, time required for use, confidence, and training needed. Qualitatively, we will explore *PrEP My Way* in accordance with the Unified Theory of Acceptance and Use of Technology (UTAUT; Figure 5) in up to 20 participants purposively selected to

Figure 5. Unified Theory of Acceptance and Use of Technology

reflect high and low usage of the kits. Questions for each model component are described in Table 3.

All quantitative data will be recorded on encrypted tablets in REDCap. Qualitative interviews will be digitally recorded and transcribed. All data will be collected in a private space using the participant's preferred language (KiSwahili, DhoLuo, or English).

Table 3. Questions to be used in assessing PrEP My Way acceptability	
Model component	Question content
Performance expectancy	Perceived usefulness, personal outcome expectations
Effort expectancy	Perceived effort needed to arrange delivery and use the kit components
Social influence	Perceived norms and stigma
Facilitating conditions	Kit delivery, instructional materials, role of the peer
Behavioral intention to use	Attitudes around current and anticipated future use/non-use
Actual use	DBS tenofovir concentration

Participants will then be disenrolled from the study and linked back to the Lumumba Clinic, Kisumu County Hospital, or a similar clinic of their choice, for continuation of PrEP as desired. A small incentive/thank you gift (worth a minimum of ~500 Kenyan Shilling or \$5 US) will be given at that time for transport and completion of study-related activities (not *PrEP My Way* utilization). The estimated time spent with the participant will be ~2 hours at enrollment, 30 minutes at Months 1 and 3, and ~1 hour at Month 6.

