Control condition. After randomization, a study research assistant (RA) will administer the baseline demographic and socio-behavioral questionnaire. Control participants will then continue to receive PrEP and any other desired sexual health services at Lumumba Clinic or Kisumu County Hospital. The study may provide or assist the clinics in obtaining necessary supplies for routine HIV/STI services in the event of supply chain stock outs. The RA will call the control participant in ~3 months to maintain accurate contact information and remind her that the RA will meet her at her 6-month PrEP appointment in the Lumumba Clinic or Kisumu County Hospital for the final study visit. The RA will make a reminder call one week in advance. If the control participant does not wish to continue PrEP or return to the Lumumba Clinic/Kisumu County Hospital, she may come to the RCTP study site for the final study procedures. The RA will then collect the following using the methods described above:

- Dried blood spot for tenofovir concentration
- Socio-behavioral data (quantitative questionnaire)
- Review of Lumumba Clinic/Kisumu County Hospital chart records for HIV and STI testing and pick up of PrEP and contraception; participants may be asked for clarification if chart records are incomplete

Control participants will then be disenrolled and provided with a small incentive/thank you (worth at least~500 Kenyan Shillings or \$5 US) for completion of study-related activities. They will continue to receive PrEP and other sexual health services at Lumumba Clinic, Kisumu County Hospital, or another clinic as desired.

Peer identification and hiring, and oversight. Peers will not be participants. They will be identified from PrEP programs in the Kisumu region. Peers will be 18-30 years old women who have themselves taken PrEP for at least 3 months and are fluent in KiSwahili, DhoLuo, and/or English. If they do not own a smart phone, the study will provide one for showing the *PrEP My Way* video guidance and enabling two-way communication with participants (e.g., SMS, WhatsApp). Although already experienced with PrEP, all peers will be trained about PrEP using Kenyan national guideline materials [35]. They will also undergo sensitivity training, including

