Feasibility. Feasibility will be assessed by the following metrics: 1) receipt of the *PrEP My Way* kit at Months 1, 3, and 6, and 2) ability of the participant to use each aspect of the kit (i.e., the HIV self-test, use of the vaginal swab, and self-administration of medroxyprogesterone [if desired]) per protocol. The intervention will be considered feasible if $\geq 70\%$ (35/50) participants 1) receive a kit and 2) achieve a readable HIV test, usable vaginal swab, and self-injection of medroxyprogesterone, if desired, at $\geq 66\%$ (2/3) of visits.

Acceptability. The *PrEP My Way* intervention will be considered acceptable if $>70\%$ (35/50) participants rate 70% (7/10) items on the SUS as "very good" or higher. The qualitative interview will delve deeply into each of the four domains of the UTAUT model to provide in depth feedback on the intervention.

Primary outcomes- Preliminary impact on PrEP adherence and program retention at 6 months. PrEP adherence will be assessed primarily by DBS for tenofovir diphosphate (TFV-DP) concentration. The TFV-DP concentration will provide an estimate of doses taken over the prior 3 months (see Table 4; [11, 50]). Retention will be assessed by kit receipt in the intervention arm and clinic attendance per clinic records in the control arm at Month 6. Potential influencing and mediating socio-behavioral factors (Table 2) will be explored.

Secondary outcomes. We will assess the following:

Table 4. TFV-DP concentrations in DBS	
Estimated use	Median fmol/punch (IQR)

- Self-reported PrEP adherence at Months 1, 3, and 6 (intervention arm) and Month 6 (control arm). We will use the 3-item scale developed by Wilson et al, which involves different recall tasks (frequency, percent, and rating of adherence) over the prior 30 days [51]
- PrEP persistence over the 6-month period
- Rates of STI testing at Months 1, 3, and 6
- Rates of pregnancy test and contraception pick up at Months 1, 3, and 6
- Cost estimates

Protective*	>1,250
Moderate	900-1,249
Low	<900

*Exact value to be explored (see text)

Analysis

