Primary outcomes. Adherence (as determined by TFV-DP concentrations in DBS) and program retention at 6 months will be analyzed descriptively and then compared between the two study arms using Chi-square tests (i.e., comparing protective TFV-DP concentrations versus not; retained versus not). DBS will be shipped to the University of Cape Town in South Africa and some will be tested to measure TFV-DP concentrations. We will use an intention-to-treat approach for the primary outcomes but will also perform per protocol analysis. Because of the developmental nature of this R34 study and the small sample size, we will assess potential influencing factors on adherence and retention using logistic regression models. Thresholds from protective TFV-DP concentrations may be explored, as this is an active area of research [53, 54]. We will pre-specify variables to avoid overfitting the models as age, self-esteem, empowerment, stigma, depression, and alcohol/substance use. We will analyze study outcomes by peer to look for any clustering effects. We will also explore empowerment and depression as mediators of the relationship between the *PrEP My Way* intervention and adherence and retention outcomes, using the approach by Valeri and VanderWeele, which allows for logistic modeling, and sensitivity analyses around key assumptions per Imai.[55].

Secondary outcomes. We will use descriptive statistics to understand self-reported adherence, PrEP persistence, early retention, and rates of STI testing, pregnancy testing, and contraception pick up. We will also explore trends for self-reported adherence within the intervention group with regression analysis. We will compare all secondary outcomes between intervention and control arms with Chi-square tests (categorical variables) and t-tests (continuous variables). As described above, we will also explore in the influence of age, self-esteem, empowerment, stigma, depression, and alcohol/substance use on any observed differences through logistic and linear regression models, for dichotomous and continuous variables, respectively.

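### Services obtained outside the assigned channel are not recorded systematically or alike in both arms, so comparisons of PrEP persistence and service uptake can miss them unequally

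*Combined protocol and SAP*

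**What the plan says.** The plan takes service data from a different source in each arm.

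- **Controls** (Aim 2, Control condition). The Month 6 collection includes "Review of Lumumba Clinic/Kisumu County Hospital chart records for HIV and STI testing and pick up of PrEP and contraception", with the proviso that "participants may be asked for clarification if chart records are incomplete". No other facility is named, and the footnote to Table 1 limits the word clinic to the same two.
- **Intervention arm** (Aim 2, Intervention condition). At kit delivery, "The peer will obtain the HIV test results and document PrEP and contraception use". At Month 6, "an RA will collect the following data either in the field or at the study site". The list that follows has the dried blood spot (DBS), creatinine, the socio-behavioural questionnaire and acceptability data, but no chart review.
- **Both arms** (Table 2). The questionnaire domains include no item on where PrEP, tests or contraception were obtained.
- **Outcomes** (Outcome measures). "Retention will be assessed by kit receipt in the intervention arm and clinic attendance per clinic records in the control arm at Month 6". Persistence, STI testing, and pregnancy-test and contraception pick-up are secondary outcomes. Persistence has no stated data source or scoring rule; the Power section adds only that all six months enter the denominator.
- **Comparison** (Analysis, Secondary outcomes). "We will compare all secondary outcomes between intervention and control arms". Retention is also compared between arms, by Chi-square test.

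The plan itself makes care elsewhere foreseeable. The study-setting text describes PrEP as "available at no charge through Lumumba Clinic and other public facilities". The residence limit is a "maximum of 20 km from our study offices at RCTP". The Control condition section provides for controls who do not want to go back to the two clinics.

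**The concern.** Each arm is observed mainly through the channel to which it was assigned. A control who refills at a third facility leaves no trace in the two sets of charts. An intervention woman who misses a kit and goes to the clinic where she started PrEP leaves no trace in the peer's record, and nobody is told to open her chart.

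The two blind spots differ in kind. The kit is brought to a place the woman chooses, whereas control care is visible only at two fixed sites. Nothing suggests that the two losses would be equal or would cancel. An observed difference in persistence or uptake could then reflect where care was recorded as well as whether it was received. That matters because the pilot's results are meant to inform a fully powered trial. The per-protocol analysis planned for the primary outcomes would also need crossover information that is not collected in a set way.

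**Working it through.** The plan states no figure on this point, so the check is mainly textual, followed by arithmetic on how much one woman counts.

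**1. What would record an off-channel service?**

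| Case | Route in the plan | Does it require a record? |
|---|---|---|
| Control refills at a third facility | Optional clarification when charts are incomplete | No. A chart with no visits after transfer need not look incomplete |
| Intervention woman misses a kit and refills at a clinic | Peer's record at kit delivery | No. It is made only when a kit visit takes place |
| Either woman misses an appointment | Contact by retention teams (Participant retention and withdrawal) | No. Recording of outside services is not mentioned |
| Either woman still takes PrEP | DBS drug level; self-reported adherence at Month 6 | Shows drug-taking, but not source, testing or contraception |

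No route obliges staff to ask about outside services in both arms.

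**2. Which outcomes are exposed?**

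- DBS adherence: not exposed, because the assay reads drug from any source.
- STI testing, and pregnancy-test and contraception pick-up: exposed.
- PrEP persistence: exposed if it is scored from charts and kit records. The plan does not say how it is scored.
- Retention: defined by channel. A control seen only at a third facility counts as not retained.

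**3. Weight of one misclassified woman**, as 1 / (women per arm):

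- Power section: 80 analysed, so 80 / 2 = 40 per arm; 1/40 = 2.5 points.
- Up to 150 randomised with 20% loss: 150 × 0.80 = 120, so 60 per arm; 1/60 ≈ 1.7 points.

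**4. Illustration only.** Let u be the share of in-care women in an arm who are served off channel and unseen. The documents give no value, so I take 0 to 20% as an assumption. Observed rate = true rate × (1 − u).

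- True rate 50% in both arms, u = 10% in one arm: 50% × 0.90 = 45%, a spurious 5 points.
- The same with u = 20%: 50% × 0.80 = 40%, a spurious 10 points.
- u = 20% in both arms: 40% against 40%, no difference.
- True rates 40% (control) and 60% (intervention), assumed for the affected outcome: the true difference is 20 points. With u = 20% in controls only, 60 − 32 = 28. In the intervention arm only, 48 − 40 = 8. In both, 48 − 32 = 16.

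The error can inflate, shrink or create a difference, depending on which arm loses more.

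**The case against.** The case against has several good parts.

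- **Retention.** A reader might infer that retention is miscounted whenever a woman crosses over. The outcome is programme retention, and the plan defines it by the assigned channel. An intervention woman who refills at the clinic has left the kit programme, so counting her as not retained follows the definition, and chart review alone would not change it. This stands. Retention on PrEP from any source is a different quantity.
- **Safeguards.** A reader might infer that off-channel care is not captured at all. That is too strong: controls may be asked for clarification, the research assistant telephones controls at about three months and meets those who attend at Month 6, peers keep records, and retention teams make contact. These are real but partial.
- **Adherence.** A reader might infer that the whole preliminary-impact assessment is affected. The DBS outcome is not.
- **Scoring.** The documents do not say that a woman with an unseen refill is scored as having stopped PrEP. Persistence simply has no rule. This stands, and it is a reason to write one.
- **Clinic contact in the intervention arm.** The as-needed clinic follow-up is illustrated by treatment after a positive test, not by refills, and the repeat STI test is offered by the study itself. Neither shows that such services would go uncounted.
- **Context.** This is a pilot, the Cost section says effectiveness is not its aim, and the uptake outcomes are secondary. This lowers the stakes, but the comparisons are still planned.

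**Conclusion.** The concern holds in a limited form. The plan lacks a systematic record, alike in both arms, of services obtained outside the assigned channel. Comparisons of persistence, STI testing, and pregnancy-test and contraception pick-up can therefore miss such care unequally, and a control who moves to a third facility counts as not retained.

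The size and direction are unknown. One misclassified woman is worth 2.5 points at 40 per arm or about 1.7 at 60. The 5 to 10 spurious points shown above rest on an assumed 10 to 20% unseen in one arm and a true rate of 50% in both.

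A reader might go further and conclude that the design favours the kit, or set such a figure against the 20-point example in the Power section. The documents support neither step. They give no crossover or transfer rate for either arm, unseen care in the intervention arm would pull the other way, and the Power section concerns adherence, which does not depend on the channel.

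**What to change.** 1. At Month 6, carry out the chart review at Lumumba Clinic and Kisumu County Hospital for all randomised women, not for controls only.
2. Add a short Month 6 item in both arms: where and when PrEP, HIV and STI tests, and contraception were obtained since enrolment.
3. Write a rule for persistence, and define persistence and service uptake by any source in both arms.
4. Keep programme retention as defined, and report retention on PrEP from any source beside it.

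The cost is chart review for the second arm at clinics whose charts are already being read, plus a few questions at an existing visit. The drawback is that care at other facilities would rest partly on self-report.

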Analysis. To analyze the interviews and focus group discussions, we will use a framework approach, described in Richie and Spencer [41], which involves systematic coding to identify and define concepts, map the concepts, create typologies, find associations between concepts, and seek explanations from the data. We will use Dedoose (Version 8.0.35) for coding data. Double coding will ensure that interpretations of quotes are consistent, and that data quality is rigorous and transparent; differences between coding will be resolved by discussion involving other members of the research team. Recurring issues, concepts, and patterns will be identified using both inductive and deductive reasoning. Analyses will consider whether findings differ by age and/or language.

Summary/deliverable. This aim will produce a young woman-centered kit with pictorial and video guidance for peer-delivery of PrEP, STI testing, and contraception that is ready for assessment in Aim 2.

[figure not shown]
Aim 2. Assess *PrEP My Way* for feasibility, acceptability, and preliminary impact on PrEP adherence and program retention

Overview. We will randomize up to 150 Kenyan women (age 16-24) to *PrEP My Way* versus standard of care (i.e., clinic-based delivery of PrEP and sexual health services) and follow them for 6 months. Feasibility will be assessed by receipt of the kit at 1, 3, and 6 months and ability to use its components per protocol. Acceptability will be determined through a mixed-methods interview at 6 months. Preliminary impact will be evaluated by dried blood spot tenofovir levels (adherence) and kit use/clinic attendance at 6 months (retention) as primary outcomes.

Potential influencing and mediating socio-behavioral factors will be explored with questionnaires at enrollment and 6 months. See Figure 4 for an overview of the participant flow.

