Participants will be consented as described in Aim 1, enrolled, and randomized (1:1) using a computer-generated simple randomization sequence to receive *PrEP My Way* or follow up as usual at Lumumba Clinic or Kisumu County Hospital over the next 6 months. The code creating the random allocation order will be generated and maintained by the study analyst (separate from the investigators). A variable size block randomization scheme will be implemented to produce the randomization list. Randomization will be implemented by transcribing onto paper within numbered envelopes. Thus, neither participants nor study staff will be blinded to each participant's randomization arm assignment. Fidelity of randomization will be confirmed with tracking in REDCap.

Study procedures (Some aspects of the planned procedures may change pending input from Aim 1 findings). Study procedures for both arms are summarized in Table 1.

Table 1. Summary of study procedures by arm. Each cell indicates how/where the procedure will take place.								
	M0	M1	M3	M6	M0	M1	M3	M6
	PrEP My Way				Control			
Education (PrEP, sexual health)	Clinic	Peer	Peer	Peer	Clinic	Clinic	Clinic	Clinic
HIV testing	Clinic	Kit	Kit	Kit	Clinic	Clinic	Clinic	Clinic
PrEP	Clinic	Kit	Kit	Kit	Clinic	Clinic	Clinic	Clinic
STI sampling	Clinic [^]	Kit	Kit	Kit	Clinic [^]	Clinic [^]	Clinic [^]	Clinic [^]
Pregnancy testing; contraception	Clinic	Kit	Kit	Kit	Clinic	Clinic	Clinic	Clinic
Questionnaire administration	RA	--	--	RA	RA	--	--	RA
Acceptability scale and interview	--	--	--	RA	--	--	--	--
DBS	--	--	--	RA	--	--	--	RA

Clinic=Lumumba Clinic or Kisumu County Hospital; [^]STI testing done only in the setting of symptoms; RA = research assistant; time and motion studies will also be done at the KEMRI Research Care and Training Program (i.e., the study site), Lumumba Clinic, and Kisumu County Hospital mid-way through the study period

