Our power calculations are based on 80 participants, given an expected loss to follow-up of 20% (estimated from our current MPYA study). As shown in Figure 6, assuming a standard deviation of 10%, 80 participants will have limited power to detect a difference of 20% between the study arms (e.g., ~40% power if the primary outcome is seen in 40% of the control group versus 60% in the intervention group; see the circled green dot). If a stronger effect is seen (e.g., closer to the ideal target of 40%), we may achieve >80% power. We believe this sample size is appropriate for the development of the *PrEP My Way* intervention. If the intervention is also found to be feasible and acceptable, we look forward to fully testing the intervention in a subsequent, fully powered study.

[figure not shown]
Participant retention and withdrawal

Participants will be tracked primarily through peers (intervention) and the clinic visits (standard of care). Individuals missing scheduled appointments will be contacted through study retention teams. Participants will be able to withdraw from the study at any time.

Ethical Considerations

Human subjects

Figure 6. Estimate power for the study sample size

This study will involve young Kenyan women in two sets of study procedures to develop and preliminarily test the *PrEP My Way* intervention.

- Intervention development (Aim 1). We will use a client-centered approach, involving individual interviews and two focus group discussions with up to 25 Kenyan women to optimally design the *PrEP My Way* kit (with instructional materials) and peer delivery system (including communication and kit delivery plans).
- Pilot randomized controlled trial (Aim 2). We will randomize 150 Kenyan women to *PrEP My Way* versus standard of care (i.e., clinic-based delivery of PrEP and sexual health services) and follow them for 6 months. These participants will be distinct from those participating in the intervention development aspects of the study. Feasibility will be assessed by receipt of the kit at 1, 3, and 6 months and ability to use its components per protocol. Acceptability will be determined through a mixed-methods interview at 6 months. Preliminary impact will be evaluated by dried blood spot tenofovir levels (adherence) and kit use/clinic attendance at 6 months (retention) as primary outcomes. Mediators and moderators of PrEP use (e.g., empowerment and mental health) will be explored through questionnaires at baseline and 6 months.

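### The acceptability cut-off contradicts its own count (35/50 is not above 70%), and both pilot cut-offs print counts for 50 intervention women where the current text gives up to about 75

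*Combined protocol and SAP*

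**What the plan says.** The combined protocol and SAP sets two pass marks under Outcome measures.

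- **Feasibility:** at least 70% of women, printed as "35/50) participants 1) receive a kit and 2) achieve a readable HIV test, usable vaginal swab" and, where wanted, contraceptive self-injection, at two of three visits.
- **Acceptability:** more than 70% of women, printed as "35/50) participants rate 70% (7/10) items on the SUS as" very good or better. SUS is the ten-item usability scale.

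The size of the trial is given in several places.

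- The Aim 2 overview: "We will randomize up to 150 Kenyan women (age 16-24". The same ceiling appears in the summary and the specific objectives.
- Human subjects, without the ceiling: "We will randomize 150 Kenyan women".
- Consent, enrollment, and randomization: "enrolled, and randomized (1:1) using a computer-generated simple randomization sequence".
- Power: "Our power calculations are based on 80 participants, given an expected loss to follow-up of 20" per cent.
- Peer identification and hiring, and oversight: three peers, each serving 15 to 20 women.

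The usability scale is among the Month 6 items: "Additionally, at the Month 6 visit, an RA will collect the following data either in the field or at the study site". The Analysis section says that feasibility and the scale will be summarised descriptively. It names intention-to-treat for the primary outcomes only.

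**The concern.** One count cannot be the smallest passing result for both an at-least rule and a more-than rule with the same percentage and denominator. As printed, a team that sees 35 of 50 favourable ratings can call the intervention acceptable by the count and not acceptable by the percentage.

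The denominator raises a second problem. No section limits these criteria to a subset of 50, and half of 150 is 75. The printed counts therefore appear to come from a smaller plan than the one now described.

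These are the plan's stated criteria for judging the intervention, and the Power section refers to them when looking ahead: "If the intervention is also found to be feasible and acceptable, we look forward to fully testing the intervention". A pass mark should have one reading before the data are seen.

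**Working it through.** **Rule used.** For n women, the smallest count that is at least 70% is 0.70n rounded up to a whole number. The smallest count above 70% is the whole-number part of 0.70n, plus 1.

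**Step 1: the printed count.** 35/50 = 0.700 exactly. The feasibility figure is reproduced: at least 70% of 50 is 35. The acceptability figure is not: more than 70% of 50 is 36 (36/50 = 0.720).

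**Step 2: where 50 comes from.** 80/(1 − 0.20) = 100 randomised, or 50 per arm. The caseload agrees: 3 × 15 = 45 and 3 × 20 = 60, a range that contains 50 but not 75. With 150 randomised, the same 20% loss would leave 150 × 0.80 = 120 evaluable women, not 80.

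**Step 3: thresholds by denominator.**

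| Women in denominator | 70% of it | Smallest count, at least 70% | Smallest count, more than 70% |
|---|---|---|---|
| 40 (50 less 20%) | 28.0 | 28 | 29 |
| 50 (100 randomised) | 35.0 | 35 | 36 |
| 60 (75 less 20%) | 42.0 | 42 | 43 |
| 75 (150 randomised) | 52.5 | 53 | 53 |

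At 75, 53/75 = 70.7% and 52/75 = 69.3%, so both signs need 53. The sign matters only when 70% of the denominator is a whole number, that is, when the denominator is a multiple of 10, and then only for a result exactly at 70%. With 50 women and a true rate of 70%, the chance of exactly 35 is P(at least 35) − P(at least 36) = 0.569 − 0.447 = 0.122.

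**Step 4: the denominator for the usability scale.** The documents give an expected overall loss of 20% but no rate for a missing scale, so the loss rates here are assumptions. Take 75 women allocated and the at-least-70% rule; among all 75, 53 are needed.

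| Assumed loss | Women with a scale | Needed among them | Counts that pass among them but fail among all 75 |
|---|---|---|---|
| 10% (67.5) | 67 or 68 | 47 or 48 | 47 or 48, up to 52 |
| 20% | 60 | 42 | 42 to 52 |
| 30% (52.5) | 52 or 53 | 37 or 38 | 37 or 38, up to 52 |

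At 20% loss, 42 favourable ratings are 42/60 = 70.0% of women with a scale but 42/75 = 56.0% of those allocated.

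**The case against.** The strongest reply is that nothing of substance is wrong. The percentage comes first and the count is an illustration in brackets, so the rule carries over to any arm size. The figure of 150 is mostly stated as a ceiling, so 50 per arm remains possible. The randomisation text mentions both a simple sequence and variable blocks, so exactly 75 is not assured even at 150. At 75 the two signs agree. The criteria are descriptive, acceptability also has a qualitative part, and the primary outcomes do not depend on either.

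Most of this stands, and it limits the severity. It does not remove the conflict between more than 70% and 35/50 at the one denominator the plan prints. Nor does it explain a count for 50 where Human subjects states 150 flatly.

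Three stronger readings are tempting, and the documents do not support them:

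- A reader might infer that 35 successes among 75 women would pass, which is 35/75 = 46.7%. Nothing says that the count overrides the percentage.
- A reader might infer from the printed 50 that the scale is judged among all women allocated, since 20% loss from 50 would leave 40, and hence that a missing scale is a failure. The wording can equally mean women who gave a rating. Counting missing scales as failures would require 53 of 60, or 88%, of raters at an assumed 20% loss. That mixes retention, already a primary outcome, into a usability rating.
- A reader might infer a formal go/no-go rule for the next trial. The Power section only expresses an intention.

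**Conclusion.** The point holds and is minor. The acceptability rule contradicts its own count: 35/50 is 70.0%, and more than 70% of 50 needs 36. The feasibility rule is consistent at 50. Both counts rest on 50 intervention women, which agrees with the power and peer-caseload text but not with 150 randomised 1:1. With 75 in the arm, the threshold is 53 under either sign.

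The figure of 53 assumes that 150 are randomised and split evenly. The documents do not say whether 100 or 150 is the working size, so this review does not choose between them. A PDF-reading fault in the sign cannot be excluded, but it is unlikely because the at-least sign survives in the feasibility paragraph just before.

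The choice of denominator for the usability scale is simply unstated. It could affect the conclusion over a wider range than the sign does, but how wide depends on assumed loss.

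**What to change.** 1. Use at least 70% in both criteria. It matches the feasibility rule and is the only sign under which the printed 35/50 is correct.
2. State that the percentage governs, and print the count for the actual arm size: 53/75 if 150 are randomised, 35/50 if 100.
3. Reconcile that count with the Power section (80 evaluable) and the peer caseload (45 to 60 women), so that one sample size runs through the document.
4. State the denominator for the usability-scale criterion. Report the proportion among all women allocated to the intervention and among those with a Month 6 scale. There is no need to require that a missing scale count as a failure.

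The first, second and fourth items are wording only and need no further data or participants. Moving acceptability to at least 70% lets a result of exactly 70% pass and changes nothing else. The third item means deciding which sample size is in force and updating the text that depends on it.
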